#### 6 Treatment

# 6.1 Investigational and control drugs

The investigational study drug used in the course of this trial is deferasirox (ICL670, Exjade®) provided as 125 mg, 250 mg, and 500 mg dispersible tablets for oral use. As a control medication, placebo matching to each of the strength of active compound will be utilized.

# 6.1.1 Study drug

Deferasirox (ICL670, Exjade®) and matching placebo will be provided as 125 mg, 250 mg, and 500 mg dispersible tablets packaged in bulk high density polyethylene (HDPE) bottles with induction seals and child resistant closures. Study medications will be blinded, i.e. placebo will be formulated and packaged to be indistinguishable from the 125 mg, 250 mg, and 500 mg tablets of deferasirox.

Bottles of 35 tablets of each strength of deferasirox or corresponding placebo will be prepared, labeled and supplied by Novartis Drug Supply Management (DSM) to the local Country Pharma Organizations (CPOs) for further distribution to the study centers.

Each study site will be supplied by Novartis with study drug in identically-appearing packaging. One component of the packaging has a 2-part label. Each part of this label contains a medication number corresponding to one of the treatment groups. Investigator staff will identify the study drug package to dispense to the patient by contacting the IVRS/IWRS and obtaining the medication number(s). Immediately before dispensing the package to the patient, investigator staff will detach the outer part of the label from the packaging and affix it to the source document (Drug Label Form) containing the patient's unique patient number.

Medication labels will comply with the legal requirements of the countries where the study is implemented and be printed in the local language. They will supply no information about the patient. Only the subject identifier will be entered on the medication label by the investigator or pharmacist before the corresponding medication is handed out to the patient. The storage conditions and the expiration date for study drug will be described on the medication label.

# 6.1.2 Preparation and storage

## **6.1.2.1** Study drug

Study medication (deferasirox or placebo) must be taken once daily on an empty stomach at least 30 minutes before food consistently at the same time every day.

The tablets are dispersed by stirring in a glass of water, orange or apple juice (100 ml to 200 ml) until a fine suspension is obtained. Patients should be instructed to rinse any remaining residue from the glass with a small amount of water, orange or apple juice and drink this as well.

Having completed the screening period, patients enrolled and randomized to deferasirox (ICL670, Exjade®) or matching placebo will begin study treatment. The following dosing schedule is to be followed:

- 10 mg/kg/day (once daily) for 2 weeks, followed by 20 mg/kg/day (once daily) ( Week 2-End of treatment)
- After 3 months of treatment at the dose of 20mg/kg/day the dose can be adjusted by 5 or 10 mg/kg/day up to 40 mg/kg/day based on serum ferritin response (see Section 6.7.1.2).

The dose of 10 mg/kg/day given for the first 2 weeks of treatment has been implemented in order to reduce the risk of such adverse reactions as diarrhea, nausea, vomiting, and abdominal pain.

Patients will be instructed to take the assigned amount of drug and will be obliged to return all unused study medication at their next visit. Study medication returned by the patient will be counted and unused tablets will be recorded by the investigator/pharmacist involved in the study.

Drug accountability will be noted by the field monitor during site visits and at the completion of the trial.

Table 6-1	Dosing table for	5 mg/kg/d for	deferasirox or	placebo

Pt Weight in Kg	Closest Dose	125 mg	250 mg	500 mg	
35-37	125	1			
38-62	250		1		
63-87	375	3			
88-112	500			1	
113-132	625	1		1	
> 132	625	1		1	

Table 6-2 Dosing table for 10 mg/kg/d for deferasirox or placebo

Pt Weight in Kg	Closest Dose	125 mg	250 mg	500 mg
35-43	375	3		
44-56	500			1
57-68	625	1		1
69-81	750		1	1
82-93	875	3		1
94-106	1000			2
107-118	1125	1		2
119-131	1250		1	2
132	1375	3		2
> 132	1375	3		2

Table 6-3 Dosing table for 15 mg/kg/d for deferasirox or placebo

	_		-		
Pt Weight in Kg	Closest Dose	125 mg	250 mg	500 mg	
35-37	500			1	
38-45	625	1		1	
46-54	750		1	1	
55-62	875	3		1	
63-70	1000			2	
71-79	1125	1		2	
80-87	1250		1	2	
88-95	1375	3		2	
96-104	1500			3	
105-112	1625	1		3	
113-120	1750		1	3	
121-129	1875	3		3	
130-132	2000			4	
>132	2000			4	

Table 6-4 Dosing table for 20 mg/kg/d for deferasirox or placebo

Pt Weight in Kg	Closest Dose	125 mg	250 mg	500 mg
35-40	750		1	1
41-46	875	3		1
47-53	1000			2
54-59	1125	1		2
60-65	1250		1	2
66-71	1375	3		2
72-78	1500			3
79-84	1625	1		3
85-90	1750		1	3
91-96	1875	3		3
97-103	2000			4
104-109	2125	1		4
110-115	2250		1	4
116-121	2375	3		4
122-128	2500			5
129-132	2625	1		5
> 132	2625	1		5

Table 6-5 Dosing table for 25 mg/kg/d for deferasirox or placebo

	_		-		
Pt Weight in Kg	Closest Dose	125 mg	250 mg	500 mg	
35-37	875	3		1	
38-42	1000			2	
43-47	1125	1		2	
48-52	1250		1	2	
53-57	1375	3		2	
58-62	1500			3	
63-67	1625	1		3	
68-72	1750		1	3	
73-77	1875	3		3	
78-82	2000			4	
83-87	2125	1		4	
88-92	2250		1	4	
93-97	2375	3		4	
98-102	2500			5	
103-107	2625	1		5	
108-112	2750		1	5	
113-117	2875	3		5	
118-122	3000			6	
123-127	3125	1		6	
128-132	3250		1	6	
> 132	3375	3		6	

Table 6-6 Dosing table for 30 mg/kg/d for deferasirox or placebo

Pt Weight in Kg	Closest Dose	125 mg	250 mg	500 mg
35	1000			2
36-39	1125	1		2
40-43	1250		1	2
44-47	1375	3		2
48-52	1500			3
53-56	1625	1		3
57-60	1750		1	3
61-64	1875	3		3
65-68	2000			4
69-72	2125	1		4
73-77	2250		1	4
78-81	2375	3		4
82-85	2500			5
86-89	2625	1		5
90-93	2750		1	5
94-97	2875	3		5
98-102	3000			6
103-106	3125	1		6
107-110	3250		1	6
111-114	3375	3		6
115-118	3500			7
119-122	3625	1		7
123-127	3750		1	7
128-131	3875	3		7
132	4000			8
> 132	4000			8

Table 6-7 Dosing table for 35 mg/kg/d for deferasirox or placebo

Tubic o i	Booming table for	oo mg/kg/a loi	aciciasii ox oi pic	10000
Pt Weight in Kg	Closest Dose	125 mg	250 mg	500 mg
35-37	1250		1	2
38-41	1375	3		2
42-44	1500			3
45-48	1625	1		3
49-51	1750		1	3
52-54	1875	3		3
55-59	2000			4
60-62	2125	1		4
63-66	2250		1	4
67-69	2375	3		4
70-73	2500			5
74-76	2625	1		5
77-80	2750		1	5
81-84	2875	3		5
85-88	3000			6
89-91	3125	1		6
92-94	3250		1	6
95-98	3375	3		6
99-101	3500			7
102-105	3625	1		7
106-108	3750		1	7
109-112	3875	3		7
113-116	4000			8
117-119	4125	1		8
120-123	4250		1	8
124-126	4375	3		8
127-130	4500			9
131-132	4625	1		9
> 132	4625	1		9

Table 6-8 Dosing table for 40 mg/kg/d for deferasirox or placebo

Pt Weight in Kg	Closest Dose	125 mg	250 mg	500 mg
35	1375	3		2
36-39	1500			3
40-42	1625	1		3
43-45	1750		1	3
46-48	1875	3		3
49-51	2000			4
52-54	2125	1		4
55-57	2250		1	4
58-60	2375	3		4
61-64	2500			5
65-67	2625	1		5
68-70	2750		1	5
71-73	2875	3		5
74-76	3000			6
77-79	3125	1		6
80-82	3250		1	6
83-85	3375	3		6
86-89	3500			7
90-92	3625	1		7
93-95	3750		1	7
96-98	3875	3		7
99-101	4000			8
102-104	4125	1		8
105-107	4250		1	8
108-110	4375	3		8
111-114	4500			9
115-117	4625	1		9
118-120	4750		1	9
121-123	4875	3		9
124-126	5000			10
127-129	5125	1		10
130-132	5250		1	10
> 132	5375	3		10

#### 6.2 Treatment arms

Patients will be assigned to one of the two arms in a ratio of 2:1, deferasirox or matching placebo.

# 6.3 Patient numbering

Each patient in the study is uniquely identified by a 9 digit patient number which is a combination of his/her 4-digit center number and 5-digit subject number. The center number is assigned by Novartis to the investigative site. Upon signing the informed consent form, the patient is assigned a patient number by the investigator. At each site, the first patient is assigned patient number 00001, and subsequent patients are assigned consecutive numbers

(e.g., the second patient is assigned patient number 00002, the third patient is assigned patient number 00003). The investigator or his/her staff will contact the IVRS/IWRS and provide the requested identifying information for the patient to register them into the IVRS. The assigned patient number will be entered into the "Subject ID" field on the EDC data entry screen.

Should a patient screen fail, the patient number must be recorded as a screen failure in the IVRS/IWRS within 2 days of failing entry criteria. In addition, the Screening Log and Demography eCRFs should be completed for these patients. Any serious adverse events which occurred during screening and prior to randomization should be reported. Patient numbers will never be re-issued. A patient may be re-screened at the discretion of the investigator and assigned a new patient number.

# 6.4 Treatment assignment

At baseline (Day 1, Visit 3), all eligible patients will be randomized via IVRS/IWRS to one of the treatment arms. The investigator or his/her delegate will call or log onto the IVRS/IWRS that will assign a randomization number to the patient once a series of eligibility questions are confirmed by the investigator or his/her delegate. The randomization number will be used to link the patient to a treatment arm and will specify a unique medication number(s) for the first package(s) of study drug to dispense to the patient. The randomization number will not be communicated to the caller.

Randomization will be performed using the following procedure to insure that treatment assignment is unbiased and concealed from patients and investigator staff. A patient randomization list will be produced by the IVRS provider using a validated system that automates the random assignment of patient numbers to randomization numbers. The patient randomization list will be reviewed and approved by a member of the Biostatistics Quality Assurance Group.

The randomization numbers are linked to the different treatment groups, which in turn are linked to medication numbers. A separate medication randomization list will be produced by or under the responsibility of Novartis DSM using a validated system that automates the random assignment of medication numbers to medication packs containing each of the study drugs.

In the event that a patient is late for a regular scheduled visit, the visit week that should be followed and assessments that need to be recorded on the eCRF may vary. As a rule to follow, the time interval between the current scheduled "late visit" and the next scheduled visit should be divided in half. Should patients present themselves less than mid-way between visits (<15 days), the assessments that should be taken are those for the earlier visit. Should patients present themselves  $\ge 15$  days after the scheduled visit, then the previous visit should be skipped and the next scheduled visit should be performed. In any event, future scheduled study visits must be scheduled based on the date of randomization (baseline visit) not based on the date of the previous visit.

# 6.5 Treatment blinding

Patients, investigator staff, persons performing the assessments, and data analysts will remain blind to the identity of the study treatment from the time of randomization until database lock, using the following methods:

- 1. Randomization data are kept strictly confidential until the time of final database unblinding, and will not be accessible by anyone else involved in the study with the following exceptions:
  - Independent Data Monitoring Committee (DMC) on special request only.
  - Independent statistician and programmer reporting to the DMC,
  - Investigator and patient once a patient meets a non-fatal event which is confirmed by the Endpoint Adjudication Committee (EAC).
- 2. The identity of the study treatments will be concealed by the use of study drugs that are all identical in packaging, labeling, schedule of administration, appearance, and odor.

Unblinding will only occur in the case of patient emergencies (on a per-patient basis), for regulatory reporting, and at the conclusion of the study.

# 6.6 Treating the patient

# 6.6.1 Study drug/study treatment/active control administration

The patient will be instructed how to prepare his/her daily dose from the three tablet strengths of ICL670 or placebo available (125 mg, 250 mg, 500 mg). The dose will be assigned based on the patient's weight (detailed in Table 6-1 through Table 6-8). During the scheduled visits the investigator staff will identify the study drug package(s) to dispense to the patient by contacting the IVRS/IWRS and obtaining the medication number(s). The investigator will distribute the appropriate number of study drug bottles containing tablets of 125 mg, 250 mg and/or 500 mg to the patient, including spare medication.

Each time study medication is dispensed to the patient and/or the legal guardian the investigator will provide detailed instructions on how to prepare and administer the study drug properly according to Table 6-1 through Table 6-8.

# 6.6.1.1 Study drug administration

The study medication packaging has a 2-part label. A unique medication number is printed on each part of this label which corresponds to one of the treatment arms. Investigator staff will identify the study drug package(s) to dispense to the patient by contacting the IVRS/IWRS and obtaining the medication number(s). Immediately before dispensing the package to the patient, investigator staff will detach the outer part of the label from the packaging and affix it to the source document (Drug Label Form) for that patient's unique patient number. All drug kits assigned by the IVRS will be recorded in the IVRS.

ICL670 and matching placebo should be taken daily at least 30 minutes before food, if possible consistently at the same time every morning. The tablets may be dropped into bottled water, tap water, apple juice or orange juice and gently stirred for 1 to 3 minutes until completely dispersed. Tablets should not be dispersed in carbonated liquids. For daily doses

less than 1 g, the tablets should be dispersed in at least 100 ml (3.5 ounces), and for daily doses from 1 g to 3 g, the tablets should be dispersed in at least 200 ml (7 ounces). Following full disintegration of the tablets, the liquid should be consumed promptly. Any residue in the glass and/or on the stirrer should be dispersed in additional liquid and swallowed.

# 6.6.1.2 Study combination administration

There is no combination therapy in this protocol.

#### 6.6.1.3 Placebo administration

Placebo will be administered in the same fashion as deferasirox.

# 6.6.1.4 Ancillary treatments

Any additional therapy aimed to treat iron overload during this trial (e.g. therapy with hydroxyurea, butyrate) is not allowed. Except for the study medication, no other iron chelation therapy will be administered while patients are receiving study treatment in this trial.

# 6.7 Permitted study drug adjustments

For patients who are unable to tolerate the protocol-specified dosing schedule, dose adjustments are permitted in order to keep the patient on study drug. For example, if the patient is unable to tolerate the 10 mg/kg/day dose, the investigator may decrease the dose to 5 mg/kg/day. These changes must be recorded on the Dosage Administration Record (DAR) eCRF and IVRS/IWRS. For safety concerns, the investigator may titrate study drug dose at any time during the trial.

As outlined below, study drug dose adjustments or interruptions will be implemented for specific changes in patient weight, serum ferritin, serum creatinine, ALT/AST and skin rash. In such cases, the change must always be recorded on the DAR eCRF.

The majority of dose adjustments are covered in the Section 6.7.1 below. For cases where an exceptional dose adjustment (i.e., an adjustment not covered in the following sections) is considered necessary, the investigator will send a written request to Novartis. The request must justify the dose change and provide all the supportive clinical and laboratory information for complete evaluation by Novartis. Any exceptional dose adjustment for deferasirox needs to be authorized by Novartis. A written reply will be sent back to the investigator by Novartis within 5 working days.

## 6.7.1 Dosing modifications

## 6.7.1.1 Change in patient's weight

The dose of study drug will only be recalculated using Dosing Table 6-1 through Table 6-8 during the study if the change (increase or decrease) in body weight exceeds 10% of the weight compared to the randomization visit.

# 6.7.1.2 Change in serum ferritin (SF)

Serum ferritin should be monitored monthly, and the dose adjusted every 3 months according to serum ferritin trends. Dose adjustments should be made in steps of 5 or 10 mg/kg/day to achieve the desired rate of reduction or maintenance of iron burden. As patients reach a target serum ferritin level (usually between 500 and 1000 mcg/L) the dose can be reduced by 50% to maintain the serum ferritin within the target range. For most patients, maintenance dose will be between 10-20 mg/kg/day.

If serum ferritin falls to  $\leq$ 500 mcg/L, the investigator should consider an interruption of study medication until serum ferritin rises above 500 mcg/L according to the transfusion requirement.

Dose may be increased by 5 or 10 mg/kg/day (to a maximum of 40 mg/kg/day) for patients with:

- 1. Ferritin > 500 mcg/L who have an increasing trend of ferritin after a minimum of 3 months of treatment.
- 2. Ferritin > 1000 mcg/L who fail to have a decrease in ferritin after a minimum of 3 months of treatment.

Dose must not be increased higher than 40 mg/kg/day.

If after dose reduction, a progressive increase in serum ferritin is observed, study drug may be discontinued if the investigator believes it is in the best interest of the patient. Novartis may be contacted by the investigator to discuss dosing options that fall within the protocol guidelines if the investigator so desires.

#### 6.7.1.3 Elevations in serum creatinine

For patients who develop an increase in serum creatinine  $\ge 33\%$  above their baseline value (the mean value established at screening Visits 1 and 2) resulting in a serum creatinine above the ULN, on two consecutive occasions, a minimum of 7 days apart, the daily dose will be reduced by 10 mg/kg (or 5 mg/kg in patients receiving 10 mg/kg).

If, after a dose reduction, serum creatinine remains above the ULN, a second dose reduction or treatment interruption is recommended. After an interruption, if serum creatinine falls below the age appropriate ULN on two consecutive visits, the investigator may resume therapy at 50% of the last dose and escalate cautiously.

Serum creatinine should be monitored weekly, preferably by local labs, for the first month after study drug initiation or dose modification. Results of these labs need to be entered into the CRF only if they are significantly abnormal, defined as at least a 33% increase over the baseline value.

If after dose reduction, a progressive increase in serum creatinine is observed, study drug may be discontinued if the investigator believes it is in the best interest of the patient. Novartis may be contacted by the investigator to discuss dosing options if the investigator so desires.

Caution should especially be used in patients with creatinine clearance between 40 and less than 60 mL/min, particularly in cases where there are additional risk factors that may impair renal function such as concomitant medications, dehydration, or severe infections.

Protocol No. CICL670A2302

Study medication should be discontinued in case serum creatinine increases >2 times the age-appropriate upper limit or if creatinine clearance <40 mL/min.

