- 8. Ocular and Audiometry examinations must be performed at screening, should a patient have evidence at the screening visit that the examination(s) were performed 6 months prior to screening then the examination(s) do not need to be repeated. The examination(s) can be performed at any time at the investigators discretion if symptomatically/clinically indicated, otherwise ocular and audiometry exams should be performed annually. The ocular and audiometry exams should be performed annually during the Evaluation Period.
- 9. Brain natriuretic peptide (BNP) blood sample should be obtained at baseline and at any time during the study when there is evidence of CHF
- 10. Serum ferritin: Two samples at screening done at least 14 days apart. If a transfusion is scheduled, draw serum ferritin PRIOR to transfusion or two weeks post-transfusion. The serum ferritin samples should be obtained in the absence of known infection.
- 11. Serum creatinine will be measured at Screening Visit 1 and Screening Visit 2 and the mean value will be used for eligibility criteria. Serum creatinine will also be measured weekly between the randomization visit and Week 4 visit. For the first month after initiation or modification of dose, labs may be obtained locally until the subject's next scheduled visit. Local labs need only be included on the eCRF in the case of a result that is a 33% increase greater than baseline result.
- 12. Creatinine clearance will be calculated by the central laboratory at every visit.
- 13. TSH and Free T4 will be measured at screening, annually and at study treatment discontinuation. TSH and Free T4 should be performed annually during the Evaluation Period.
- 14. At screening Visit 1 and 2 a urine sample (at least 15 ml) will be collected and sent to the central laboratory for urinary protein and urinary creatinine to assess the eligibility of the patient. Microscopic analysis will be performed only in case of positive dipstick. Dipsticks will be supplied by the central lab. Proteinuria (urinary protein /creatinine ratio) at Visit 1 and Visit 2 (screening) and then monthly during study.

	Screening		Randomization	Treatment Period												Week 372 a End of Treatment	8-day F	Evaluation c Period	Study Evaluation Completion	Survival d Follow-Up			
Visit	1	2	3 e	4 f	5	6	7	8	9	10	11	12	13	14	15	16	17	18-96	777	501	502, 503, etc.	778	701, 702, etc.

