## 7.5.5 Laboratory evaluations

A certified central laboratory will be utilized to process and provide results for the clinical laboratory tests summarized in Table 7-2. The central laboratory chosen for this study will provide instructions regarding the collection, processing and shipment of appropriate samples.

For first month after study drug initiation or dose modification, labs may be obtained locally until the subject's next scheduled visit. Local lab results only need to be entered on the eCRF in the event that the result demonstrates a significant change from baseline. A significant change in serum creatinine is defined as an increase of 33% greater than the baseline result. A significant change for ALT/AST/Total Bilirubin is defined as an increase of 2× the baseline value. For any other laboratory assessment, it is up to the Investigator's opinion if a laboratory result represents a significant abnormality. In the event that a local laboratory is used for assessing patient samples for trial purposes, the site/CRA must complete and submit the Novartis Local Laboratory Normal Ranges (LNR) form to the Data Manager.

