## 10.5.2.4 Analysis of laboratory data

For analyzing laboratory data, data from all sources (central and local laboratories) will be combined. Other than for weekly serum creatinine monitoring visits, central laboratory results are the only laboratory results that will be captured in the database.

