2.8.3 Laboratory data

All laboratory values are generally converted into SI units and the severity grade calculated using notable and extended ranges as available in the deferasirox program standards. All values from central laboratory will be used to evaluate the primary and secondary endpoints. Any tests that are performed at local laboratories will not be used for either secondary or primary endpoints evaluation; however, collected local laboratory values will be listed along with central laboratory results and also for safety tables, all values for central and local laboratory results will be considered.

The frequency of laboratory abnormalities is displayed by parameter and treatment group. Laboratory data is summarized by presenting summary statistics of raw values and absolute and relative change from baseline.

Shift tables from baseline to highest (or lowest) post baseline value are provided for hematology: hemoglobin, WBC count, absolute neutrophils and platelets, biochemistry: alanine aminotransferase (ALT), aspartate aminotransferase (AST), serum creatinine and creatinine clearance and urinalysis: urinary total protein/creatinine ratio using normal or extended ranges. Standard oncology shift tables for laboratory parameters, based on normal ranges, are also provided.

Box plots of absolute value and the absolute change from baseline in absolute neutrophils, platelets, ALT, AST, serum creatinine, creatinine clearance and urinary total protein/creatinine ratio by time points are provided. The last available value in a time point window is used.

Criteria for clinically notable and extended laboratory ranges

Parameter	Criteria
Absolute neutrophils	<1.5×10 ⁹ /L (extended range <0.5×10 ⁹ /L)
Platelets	<100×10 ⁹ /L (extended range <50×10 ⁹ /L)
ALT/AST	>5×ULN and >2×baseline value (extended range >10×ULN and >2×baseline value)
Serum creatinine	>33% increase from baseline and >ULN at two consecutive measurements at least 7 days apart
Creatinine clearance	<60 mL/min at two consecutive measurements at least 7 days apart (extended range <40 mL/min)
Urinary total protein/creatinine ratio	>1.0 mg/mg at two consecutive measurements at least 7 days apart
Total bilirubin	>2.0 mg/dL (>34.2 umol/L)

The number and percentage of patients with laboratory results (from scheduled and unscheduled visits) meeting the criteria for notable values (see table above) will be presented.

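### Local creatinine values that give a clearance below 40 mL/min need not be entered for patients starting between 40 and 53, so the planned safety count can miss transient falls

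*Protocol*

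**What the plan says.** The recording rule stands in three places in the protocol.

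- Section 6.7.1.3, on the weekly local results: they "need to be entered into the CRF only if they are significantly abnormal, defined as at least a 33% increase over the baseline value".
- Table 7-1, footnote 11: "Local labs need only be included on the eCRF in the case of a result that is a 33% increase greater than baseline result".
- Section 7.5.5: "A significant change in serum creatinine is defined as an increase of 33% greater than the baseline result". For other tests the same section leaves it to the investigator to judge "if a laboratory result represents a significant abnormality".

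Section 10.5.2.4 sets the route into the database: "Other than for weekly serum creatinine monitoring visits, central laboratory results are the only laboratory results that will be captured in the database".

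The last sentence of section 6.7.1.3, added by Amendment 5, is the stop rule: "Study medication should be discontinued in case serum creatinine increases >2 times the age-appropriate upper limit or if creatinine clearance <40 mL/min". Section 5.2 excludes patients with clearance below 40 mL/min, so 40 is the lowest value at entry.

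On the analysis side, SAP section 2.8.3 says that "for safety tables, all values for central and local laboratory results will be considered". Its table of notable and extended ranges gives creatinine clearance as "<60 mL/min at two consecutive measurements at least 7 days apart (extended range <40 mL/min" (closing bracket omitted). It plans the number and percentage of patients meeting the notable criteria, and shift tables to the lowest post-baseline clearance using normal or extended ranges. SAP section 5.3.1 derives clearance from creatinine.

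**The concern.** The entry rule uses a relative rise in creatinine. The stop rule and the SAP's extended range use an absolute clearance. Amendment 5 added the clearance limit to section 6.7.1.3, but its list of changes shows no matching change to the recording rule. For a patient who starts close to 40 mL/min, a modest rise crosses the clearance limit well before it reaches 33%.

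At stake is the completeness of a planned renal safety output in the patients nearest the limit. They lie within the 40 to under 60 mL/min group for which section 6.7.1.3 itself asks for special caution. Because the SAP derives clearance from creatinine, an unentered creatinine is lost to the table whether or not the site acted on it.

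**Working it through.** The documents state no figure for this point, so there is nothing to reproduce. The check is algebra on the SAP formula.

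**Inputs**
- Entry line: creatinine rise of 33% or more (protocol 6.7.1.3, Table 7-1 footnote 11, 7.5.5).
- Stop line and extended range: clearance below 40 mL/min (protocol 6.7.1.3; SAP 2.8.3).
- Lowest clearance at entry: 40 mL/min (protocol 5.2).
- Clearance in men: (140 - age) x weight / (0.815 x creatinine in umol/L); in women, times 0.85 (SAP 5.3.1).

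**Band.** With age and weight fixed, clearance after a rise r is baseline/(1 + r). A value below 40 with r under 0.33 needs a baseline below 40 x 1.33 = 53.2 mL/min. The rise that brings clearance to 40 is baseline/40 - 1.

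| Baseline clearance (mL/min) | Rise that reaches 40 | Clearance at a 33% rise (baseline/1.33) |
|---|---|---|
| 42 | 5.0% | 31.6 |
| 45 | 12.5% | 33.8 |
| 48 | 20.0% | 36.1 |
| 50 | 25.0% | 37.6 |
| 53.2 | 33.0% | 40.0 |
| 54 | 35.0% | 40.6 |
| 60 | 50.0% | 45.1 |

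**Weight.** If weight changes by a factor w, the upper edge is 53.2/w: 56.0 after a 5% loss (53.2/0.95) and 50.7 after a 5% gain (53.2/1.05).

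**Example** (assumed man of 75 years, 65 kg, baseline clearance 45). The numerator is 65 x 65/0.815 = 5184. Baseline creatinine is 5184/45 = 115.2 umol/L. Clearance is below 40 above 5184/40 = 129.6. Entry is required only from 115.2 x 1.33 = 153.2. A local value between 129.6 and 153.2 gives a clearance below 40 and need not be entered.

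**Samples concerned.** Only local samples in the first month after a start or dose change: Weeks 1 and 3 for a new start (Visits 3.01 and 4.01), and about three between 4-weekly visits after a later dose change.

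**Effect on the count.** The SAP does not say whether the below-40 range also needs a confirming value.
- If one value is enough, the patient is missed when the local value is the only one below 40 and every central value is 40 or more.
- If two consecutive values at least a week apart are needed, the patient is also missed when only the unentered local value and the next central value are below 40.

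**What is not touched.** A rise under 33% from the highest eligible creatinine stays below 1.5 x 1.33 = 1.995 x ULN, so it cannot meet the endpoint at 2 x ULN (same ULN assumed). SAP 2.8.3 also keeps local values out of endpoint evaluation. Creatinine is not a component of event-free survival. Time to discontinuation uses the recorded date and reason for stopping.

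**The case against.** **Nothing says that a clearance is calculated from a local sample.** Table 7-1 footnote 12 and section 7.5.5.2 give the calculation to the central laboratory. Footnotes e and f say only that it is done at Weeks 1 and 3. This stands. A reader might infer that unentered values between the two lines stop treatment; the documents do not state this. The incomplete count does not depend on it, because the SAP works from the creatinine value.

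**Central samples close most of the gap.** Weeks 1 and 3 are followed by scheduled Weeks 2 and 4. Section 6.7.5 asks for a prompt End of Treatment visit, at which Table 7-1 schedules creatinine and clearance. On the single-value reading, what remains is a fall that recovers before the next central sample. Section 1.3 reports that creatinine rises often resolved without intervention, so such falls are plausible.

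**The event is recorded elsewhere.** A finding that leads to stopping goes on the adverse event page (6.7.5), abnormal laboratory values are an End of Treatment reason (6.7.6.1), and follow-up is weekly for four weeks (6.7.2). It would be wrong to infer that stops go unrecorded. But these pages do not put a creatinine value into the laboratory dataset that the table counts.

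**The 33% rule is a minimum.** Sites may enter more, and limiting entry of weekly local results is a reasonable economy. But permission is not a requirement, and nothing directs sites to enter these values.

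**The comparison between arms may be unharmed.** If the same share is missed in each arm, the risk ratio is unchanged and only the counts are low. The documents give no ground for claiming a biased comparison.

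**Conclusion.** The point holds as a minor gap in data capture. The recording rule can leave out local creatinine values that give a clearance below 40 mL/min in patients with baseline clearance from 40 to below 53.2 mL/min. The SAP 2.8.3 below-40 count and the shift to lowest clearance can then miss transient falls.

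This rests on three assumptions: stable weight (the upper edge moves between 50.7 and 56.0 for a 5% change); Cockcroft-Gault as the SAP's adult formula; and the notable-range and shift tables being safety tables that take local values, as SAP 2.8.3 indicates.

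The documents do not give the share of patients entering in this band or how often falls are transient, so the undercount cannot be sized. No effect on event-free survival, the endpoint at 2 x ULN or time to discontinuation is claimed, and the stop rule itself is not disputed.

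**What to change.** Leave the stop rule as it is.

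1. In section 6.7.1.3, Table 7-1 footnote 11 and section 7.5.5, change the recording rule to: *Enter a local creatinine result if it is at least 33% above baseline, or gives a Cockcroft-Gault clearance below 40 mL/min, or leads to stopping or interrupting study drug.*
2. Before database lock, enter from source documents every available on-treatment local creatinine that gives a clearance below 40 mL/min. Do not restrict this to patients who were stopped, or the count stays incomplete. The search can be limited to patients with baseline clearance below about 56 mL/min, which allows for a 5% weight loss. The creatinine value is enough, since the SAP derives the clearance.

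The cost is some extra data entry and a source check in a limited group. The wording must be carried in a protocol amendment with the approvals that section 11 requires. No new sample is needed.
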